### 8.2.2. Analysis Methods

- The primary analysis will compare groups using the CMH chi-square test (the stratification factor is whether or not to perform trepanation/drainage was performed), summarize the 90-day recurrence (trepanation/drainage group) / progression rate (non-surgical group) for the MMA embolization group and the control group using the two-sided 95% CI (Clopper-Pearson method) and summarize the two-sided 95% CI for the difference in recurrence or progression rates between the two groups using the Miettinen-Nurminen method.
- Sensitivity analyses will use generalized linear mixed-effects model to calculate ORs and their 95% CIs for the comparison of recurrence or progression rates between the two arms, with group as fixed effect, site as random effect. Results of multivariable analysis will also be

presented, including treatment group, sex, age, surgical treatment strata (trepanation/drainage vs. no trepanation/drainage), any usage of antiplatelet or anticoagulant therapy, hematoma volume of baseline CT as covariates.

Enter Analysis Methods and Results Presentation

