5. Treatment in the Study

In this study, patients were stratified based on initial clinical assessments into two primary categories: those designated for burr-hole drainage and those selected for conservative treatment. Each category was then subject to further randomization. Specifically, within the burr-hole drainage category, patients were allocated into either the 'burr-hole drainage + optimal medical care + MMA embolization' subgroup or the 'burr-hole drainage + optimal medical care' subgroup. Similarly, patients initially slated for conservative treatment were randomized into 'conservative management + optimal medical care + MMA embolization' and 'conservative management + optimal medical care' subgroups.

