7.1.1 Test level

Two-sided tests are performed for all hypothesis tests ($\alpha = 0.05$). The confidence level of all confidence intervals is 95%.

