7.1.3 Estimation of sample size

This study hypothesizes that MMA embolization may reduce the recurrence (operation group) or progression (conservative treatment group) of SDH. The estimated recurrence or progression rate of hematoma in the MMA embolization group is 5%, while that of control group is 12%. When estimating bilateral 5% for the statistical significance level, 90% for power, and 8% for an acceptable rate of loss to follow-up, the total sample size is estimated to be 722 cases.

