### 8.2.3. Model Specifications

#### 8.2.3.1. Model Specifications of Primary Analysis

Statistical analysis of binary categorical variables
Endpoints and parameters

 
Endpoint: recurrence or progression rate of hematoma at 90 days after randomization
 
Parameters: 
 
Proportion estimate and 95% CI
 
Risk difference, p-value and 95% CI
 
 
 

Input Variables

 
AVAL: response variable
 
TRTAN: groups
 
COUNT: number of subjects per level per group
 
COVARIATES: adjustment Variables
 

SAS Code Sample

Example code for Clopper-Pearson 95% CI calculation:
 <pre>proc freq data = adeff;   table aval/binomial (cl = exact) alpha = 0.05 ;   weight count;   by trtan;   ods output binomialcls = binomialcl; run;</pre> 
Example code for risk difference and 95% CI calculation:
 <pre>proc freq data = adeff;   table trtanaval/riskdiff (cl = mn) chisq alpha = 0.05;   weight count;   ods output pdiffcls = diff chisq = pvalue1;</pre>

```
run;
```

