#### **SAS Code Sample:**

```
proc mi data=im1 seed=1234 n impute=20 out=im2
round=....1
min=....0
max=....1;
;
by trtan;
var sex age bmi basemrs basemth aval;
mcmc chain=multiple nbiter=200 niter=100;
run;
```

```
proc sort data=im2;
```

```
by _imputation_ trtan usubjid siteid;
run;
```

```
proc transpose data=im2 out=im2_t(rename=(_name_=avisit coll=aval));
```

```
by _imputation_ trtan usubjid siteid;  
var v1 v2;  
run;
```

```
proc sql noprint;  
create table im2_count as  
select distinct  
    _imputation_,  
    trtan,  
    avisit,  
    aval,  
    count(*) as count  
from im2_t  
group by _imputation_,trtan,avisit,aval  
order by _imputation_,trtan,avisit,aval  
;  
quit;
```

```
/*clopper-pearsen 95%ci*/  
ods select none;  
proc freq data= im2_count;  
    by _imputation_ trtan avisit;  
    table aval / binomial (cl=exact) alpha=0.05;  
    weight count;
```

```
ods output binomial=binomial;
```

```
run;
```

```
ods select all;
```

```
proc transpose data=binomial out=binomial_t;
```

```
by _imputation_ trtan avisit;
```

```
var nvalue1;
```

```
id label1;
```

```
quit;
```

```
proc sort data=binomial_t;
```

```
by trtan avisit _imputation_;
```

```
run;
```

```
ods select none;
```

```
proc mianalyze data=binomial_t;
```

```
by trtan avisit;
```

```
modeleffects proportion;
```

```
stderr ase;
```

```
ods output parameterestimates=binomial_t_pool;
```

```
run;
```

```
ods select all;
```

```
/*mn*/
```

```
proc freq data=im2_t;  
  by _imputation_ ;  
  tables trtan *aval / commonriskdiff (cl=score test=score) riskdiff (cl=mn);  
  ods output commonpdifftests=commonpdifftests1 commonpdifff=commonpdiffl  
    pdiffcls=pdiffcls1 riskdiffcol1=riskdiffcol11;  
run;
```

```
data riskdiffcol11;  
set riskdiffcol11(where=(row="difference"));  
run;  
proc sort data=riskdiffcol11;  
  by _imputation_ ;  
run;
```

```
proc mianalyze data=riskdiffcol11;  
  modeleffects risk;  
  stderr ase;  
  ods output parameterestimates=pest1_pool;  
run;
```

```
/*cmh*/
```

```
*** perform cmh test;  
proc freq data=im2_t;
```

```
tables strata*trtan*aval/cmh;  
ods output cmh=cmh;  
by _imputation_;  
run;  
*** apply wilson-hilferty transformation to the cmh statistic and  
standardize the resulting normal variable;
```

```
data cmh_wh;  
set cmh(where=(alhypothesis="general association"));  
cmh_value_wh=((value/df)**(1/3) - (1-2/(9*df))/sqrt(2/(9*df));  
cmh_sterr_wh = 1.0;  
run;
```

```
*** combine results;  

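### The primary test is stratified by the drainage/conservative category, but the confidence interval reported beside it is not, so the two can disagree in a borderline trial

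*SAP*

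**What the plan says.** Protocol 3.1 has the decision on trepanation and drainage made before randomisation. Protocol section 5 then sorts patients into drainage or conservative treatment and adds: "Each category was then subject to further randomization". Protocol 6.4 calls the list stratified but does not name the factor. The event also differs by category: recurrence after drainage, progression without it.

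SAP 8.2.2 stratifies the primary CMH chi-square test by trepanation/drainage, and the CMH step in Appendix 3 uses `strata*trtan*aval`. For the effect size, 8.2.2 asks for the "two-sided 95% CI for the difference in recurrence or progression rates between the two groups using the Miettinen-Nurminen method" and names no stratum. The code agrees with that text:

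- SAP 8.2.3.1: "table trtanaval/riskdiff (cl = mn) chisq alpha = 0.05". An operator seems to have been lost in text extraction, which is not counted here. No stratum variable appears.
- Appendix 3, imputation path: "tables trtan *aval / commonriskdiff (cl=score test=score) riskdiff (cl=mn". This requests a common risk difference, which is defined across strata, but supplies no stratum. The next step pools `risk` and `ase` from the collapsed table.

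The sensitivity odds ratio in 8.2.2 comes first from a mixed model "with group as fixed effect, site as random effect". The same bullet then adds a multivariable model that includes the surgical stratum. SAP Table 1 lists other multivariable covariates (group, sex, age, hematoma thickness, baseline mRS) and leaves the stratum out.

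**The concern.** SAP Table 4 puts the risk difference, its 95% CI and the CMH p-value on one result line, so a reader will take them as one analysis. They are not: the test respects the randomisation and the interval ignores it. The reason for change in Table 1 covers dropping time-to-event methods and adding logistic regression. It gives no ground for leaving the stratum out of the interval.

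At stake is a coherent headline result. If the effect is near the threshold, the report could carry a significant p-value beside an interval that covers no difference. SAP 9.1.2.2 carries the same method to the 360-day endpoint and to other categorical secondary endpoints.

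**Working it through.** **The plan's own figure.** Inputs from Protocol 7.1.3: 12% v 5%, two-sided 5%, "90% for power, and 8% for an acceptable rate of loss to follow-up". With pooled variance and no continuity correction:

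n = [1.96·√(2·0.085·0.915) + 1.2816·√(0.12·0.88 + 0.05·0.95)]² / 0.07² = 331.5, so 332 per arm. Then 332/0.92 = 360.9, so 361 per arm and 722 in total. The stated size is reproduced.

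**Assumptions.** The documents give no category shares or rates. Three illustrative sets, each averaging to 12% v 5% (control/embolization):

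- A: shares 50/50, rates 6%/2% and 18%/8%
- B: shares 75/25, rates 8%/3% and 24%/11%
- C: shares 80/20, rates 6%/2% and 36%/17%

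**Point estimate.** With 1:1 allocation within category, the stratum-weighted and collapsed differences are the same. For C: 0.8·(−4) + 0.2·(−19) = −7.0 points.

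**Variance at no difference, which decides whether 0 is inside the interval.** Collapsed: 0.085·0.915 = 0.0778. Stratified: the share-weighted sum of p(1−p) at each category's pooled rate.

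| Set | Stratified variance | √(collapsed/stratified) |
|---|---|---|
| A | 0.5·0.0384 + 0.5·0.1131 = 0.0758 | 1.013 |
| B | 0.75·0.0520 + 0.25·0.1444 = 0.0751 | 1.018 |
| C | 0.8·0.0384 + 0.2·0.1948 = 0.0697 | 1.057 |

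The numerators are equal and the CMH variance is smaller when category rates differ. Apart from small finite-sample factors, disagreement can therefore run only one way: CMH significant, interval including 0.

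**Interval width, Miettinen-Nurminen, 361 per arm.** The collapsed interval is −11.23 to −3.01 points, width 8.22.

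| Set | Stratified upper limit | Collapsed width relative to stratified |
|---|---|---|
| A | −3.04 | 0.3% narrower |
| B | −3.07 | 0.1% wider |
| C | −3.19 | 1.3% wider |

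A wider grid at 332 per arm used drainage shares of 50-90% and control risk in the conservative category 1-6 times that in drainage for a constant relative risk, or 1-4 times for a constant risk difference. The collapsed interval (width 8.59 points) is 1.1% narrower to 1.7% wider under constant relative risk, and 0.1% narrower to 5.4% wider under constant risk difference. For a twofold risk difference between categories it stays within 1% either way.

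**Disagreement in simulated trials (CMH p<0.05, interval includes 0).**

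- Sets A-C, 361 per arm: 0.3-1.3% at the planned effect, and 1.0-4.9% at 60% of it.
- Grid, shares 50% and 80%, 332 per arm, planned effect: at most 0.02% with equal category risks, about 0.3% with a twofold difference, 0.5-0.9% with a fourfold one. At a weaker effect (relative risk 0.55) it reaches 2.5%.
- The reverse disagreement was essentially never seen.
- No effect, fourfold difference: the collapsed interval excludes 0 in 4.0-4.4% of trials, against 4.9-5.0% rejection by CMH.

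**Odds ratio.** Without the category: (0.05/0.95)/(0.12/0.88) = 0.386. With it, 0.349-0.385 over the grid.

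**The case against.** The strongest reply is that this hardly matters. SAP section 2 ties significance to the p-value, and the planned p-value is the stratified one, so the formal decision is clear. SAP 8.3 also reports the primary endpoint by surgical stratum, so category-specific differences and intervals will be available. The code is labelled as example code, and the request for a common risk difference in Appendix 3 suggests a dropped variable rather than a choice. All of this stands, and it keeps the point minor. It does not remove the mismatch: the text of 8.2.2 names no stratum for the interval either, and subgroup intervals do not give an overall interval matched to the test.

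Three stronger readings are tempting, and the documents do not support them.

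- *The interval is too wide.* A comparison of simple standard errors for sets A-C gives excesses of 1.5%, 2.0% and 6.5%. Those are Wald-type ratios, not Miettinen-Nurminen widths. On the method the SAP names, set A reverses the sign.
- *The effect estimate does not match the test.* With 1:1 allocation within category the point estimate is essentially unchanged. Only the interval differs.
- *The sensitivity odds ratio ignores the category.* That holds only for the group-and-site model. The multivariable model in 8.2.2 includes the category, and the SAP does not rank one model above the other.

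**Conclusion.** The mismatch is certain from the text and code: the primary test is stratified, and its interval is not. The consequence is small and its size uncertain, because every figure rests on assumed category shares and rates. Over the range examined, the collapsed interval is about 1% narrower to about 5% wider. Disagreement with the test occurs in roughly 0-1.3% of trials at the planned effect and up to about 5% with a weaker one. That upper figure needs a sixfold difference in control risk between categories, for which the documents give no basis. The error is conservative, and nothing here inflates type I error.

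Two related defects also stand. After imputation, the pooled interval is built from the collapsed difference and its asymptotic standard error, so it is neither stratified nor Miettinen-Nurminen. And Table 1 and 8.2.2 disagree on whether the multivariable model contains the category. Severity: minor.

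**What to change.** - In SAP Table 1, 8.2.2, 8.2.3.1 and Appendix 3, define the primary effect as the common risk difference with a stratified Miettinen-Nurminen (score) 95% CI, tabulating `strata*trtan*aval`.
- Define the stratum as the category recorded at randomisation. The wording in 8.2.2 leaves open whether it is drainage planned or drainage performed.
- After imputation, pool the stratified estimate and its standard error instead of the collapsed `risk` and `ase`, and say what kind of interval results.
- Add the category as a fixed effect to the group-and-site model, and make the covariate lists in Table 1 and 8.2.2 agree.
- Keep the collapsed interval as descriptive only.

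The cost is SAP wording, the changed TABLES statements, the pooling inputs and one model term. No patients or new data are needed.

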### 8.2.3. Model Specifications

#### 8.2.3.1. Model Specifications of Primary Analysis

Statistical analysis of binary categorical variables
Endpoints and parameters

 
Endpoint: recurrence or progression rate of hematoma at 90 days after randomization
 
Parameters: 
 
Proportion estimate and 95% CI
 
Risk difference, p-value and 95% CI
 
 
 

Input Variables

 
AVAL: response variable
 
TRTAN: groups
 
COUNT: number of subjects per level per group
 
COVARIATES: adjustment Variables
 

SAS Code Sample

Example code for Clopper-Pearson 95% CI calculation:
 <pre>proc freq data = adeff;   table aval/binomial (cl = exact) alpha = 0.05 ;   weight count;   by trtan;   ods output binomialcls = binomialcl; run;</pre> 
Example code for risk difference and 95% CI calculation:
 <pre>proc freq data = adeff;   table trtanaval/riskdiff (cl = mn) chisq alpha = 0.05;   weight count;   ods output pdiffcls = diff chisq = pvalue1;</pre>

```
run;
```

### Example code for CMH chi-square:

```
proc freq data = adeff;
  table strata trtan / chisq alpha = 0.05;
  weight count;
  ods output chisq = pvalue1;
run;
```

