7.3 Efficacy Analysis

7.3.1 Primary efficacy analysis

Summarize the incidence of the primary endpoint event.

Primary endpoint event: incidence of recurrence (surgery group) or progression (drug therapy

group) of SDH within 90 days post-procedure

Hematoma recurrence refers that the maximum thickness of hematoma exceeding 10 mm, combined with neurological symptoms, or the patient needs to undergo re-operation (surgery group);

Symptomatic CSDH progression refers that the maximum thickness of hematoma increasing by more than 3 mm compared with baseline, or the patient requires operation (drug therapy group).

Note: The primary endpoint event is considered to have been met for any patient who died from any cause within 90 days post-procedure.

Cochran-Mantel-Haenszel (CMH) chi-square analysis will be used for primary endpoints. The difference in event incidence between the two groups and its 95% confidence interval will be calculated. The Kaplan-Meier (KM) method is further used to estimate the incidence of primary endpoint events and its 95% confidence interval.

SAS code to be used in CMH analysis is as follows:

```
ods output CMH=CMH_out;  
  
proc freq data=FatComp order=data;  
  
tables Layer*Exposure*Response /CMH ALPHA=0.05;  
  
weight count;  
  
output out=cmh_ci cmh;  
  
run;
```

Sas code to be used for KM estimation is as follows:

```
proc lifetest data=TTE alpha=0.05;  
  
time avalm*cnsr(1);  
  
strata /group=trtg;  
  
ods output Quartiles = Quartiles
```

```
ProductLimitEstimates=Estimates;  
run;
```

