**Table 4 Overview of planned primary efficacy endpoints analyses**

	Data Presentation Generated		
	Table	Figure	Listing
Incidence of recurrence (subjects with trepanation) or progression (subjects with no trepanation) of subdural hematoma within 90 days after randomization			
Number and percentage of subjects with event - Hematoma recurrence (in the trepanation/drainage group) in the MMA embolization and control arm respectively - Hematoma progression (in the non-surgical group) in the MMA embolization and control arm respectively - Death within 104 days (90 days + 14 days) in the MMA embolization and control arm respectively	Y		Y
Dichotomous data analyses:			Y

	Data Presentation Generated		
	Table	Figure	Listing

 
- Recurrence (in the trepanation/drainage group)/progression rate (in the non-surgical group) with 95% CI
 
- Difference in recurrence or progression rates between MMA embolization and control groups with 95% CI and CMH Chi-square P value
 
- OR and its 95% CI for the comparison of recurrence or progression rates between treatment and control groups
 
			

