### Presentation of Results

- Estimates of rates and 95% CIs were available for BinomialCL.
- Risk difference and 95% CI are available from diff.
- Chi-square P values are available from PVALUE1.

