#### Input Variables

- AVAL: response variable
- TRTAN: groups
- SITEID: subject site number
- COUNT: number of subjects per level per group
- COVARIATES: adjustment Variables

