#### SAS Code Sample

#### Generalized Linear Mixed-effects Model Example Code:

```
proc glimmix data=adeff descending;
  class site trtan;
  model aval/ count = trtan covariates / solution;
  random intercept / subject=site;
  ods output oddsratio= odds ratio estimates;
```

run;
Presentation of Results
• The OR and 95% CI for the ratio can be obtained from Odds Ratio Estimates.

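### SAP example code does not deliver the analyses stated in 8.2.1 and 8.2.2: no CMH p-value in 8.2.3.1, an inconsistent and unfinished imputation path, and miscounted events in the Appendix 3 GLMM

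*SAP*

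**What the plan says.** **Governing text.** SAP 8.2.2: "The primary analysis will compare groups using the CMH chi-square test", stratified by whether trepanation/drainage was performed. SAP Table 4 promises "Difference in recurrence or progression rates between MMA embolization and control groups with 95% CI and CMH Chi-square P value". Protocol 7.3.1 has code that requests it: "tables Layer*Exposure*Response /CMH ALPHA=0.05". The imputation code in SAP Appendix 3 also requests CMH on a stratum-by-treatment-by-response table.

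**SAP 8.2.3.1 code.** The risk-difference block, which has no stratum, has "ods output pdiffcls = diff chisq = pvalue1". The next block is headed CMH but asks for the CHISQ option and has "ods output chisq = pvalue1". The results section then says "Chi-square P values are available from PVALUE1".

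**Imputation path.** SAP 8.2.1 sets 10 imputations by MCMC when more than 5% of data are missing. The Appendix 3 code sets 20. It imputes by arm, transposes, runs CMH per imputation, applies a Wilson-Hilferty transformation, pools in PROC MIANALYZE and moves on.

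**Sensitivity GLMM.** SAP 8.2.3.2 defines "COUNT: number of subjects per level per group" and fits "model aval/ count = trtan covariates / solution". Appendix 3 builds the count within imputation, visit, site, arm and response level, and then uses the same response-over-count form.

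**The concern.** Where text and code disagree, a programmer has to choose, and in an open-label trial that choice should not be left until results are visible. Three things are at stake.

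- The primary p-value could come from a dataset that never holds a CMH result.
- Under imputation, the pooled p-value and the number of imputations are not fixed by the plan.
- The sensitivity OR in Appendix 3 could be pulled towards 1, so that a true primary result appears to be contradicted by its own sensitivity analysis.

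**Working it through.** **Plan's own figure.** Inputs from Protocol 7.1.3 and SAP 3: 12% vs 5%, two-sided 0.05, 90% power, 8% loss. With mean rate 0.085:

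n = [1.960·√(2·0.085·0.915) + 1.2816·√(0.12·0.88 + 0.05·0.95)]² / 0.07² = (0.773 + 0.501)² / 0.0049 ≈ 331.5, so 332 per arm. 332/0.92 = 360.9, so 361 per arm and 722 in total. The sample size reproduces and is not in dispute.

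**(1) Primary p-value.** There are two possible readings of the 8.2.3.1 code.
- *PVALUE1 keeps the unstratified chi-square.* Simulation with 332 per arm and assumed stratum shares of 20/50/80%: with equal stratum rates, power is within 0.1 point of CMH. With control rates of 28% and 8% in the two strata, it is at most 0.8 point lower, and null rejection is 4.1–4.6% against 4.8–5.1%. The effect is negligible.
- *The second block overwrites it with a three-way table.* CHISQ then gives one test per stratum, and PVALUE1 has no overall p-value to report.

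**(2) Imputation path.** The planned 8% loss exceeds the 5% trigger, so imputation is the planning case. Actual missingness may be lower, because deaths count as events and out-of-window visits are used (SAP Table 5).
- *Number of imputations:* 10 in the text, 20 in the code.
- *Stratum:* the transpose does not carry STRATA, yet the CMH step tabulates by it.
- *Tail:* with df = 1, z = (x^(1/3) − 7/9)/√(2/9). At x = 3.841 (chi-square p = 0.050), z = 1.672, the upper-tail p is 0.047 and the two-sided p is 0.094. At x = 0, z = −1.650 and the two-sided p is 0.099, although the true p is 1. Only the upper tail is evidence against the null. On complete data, a two-sided reading needs x > 4.93, an effective alpha of about 0.026, and design power falls from 0.900 to about 0.847.
- *Rounding:* the code appears to impute a normal variable by arm and round it to 0/1. Ignoring covariates, a normal with mean p and SD √(p(1−p)) exceeds 0.5 with probability 12.1% at p = 0.12 (z = 0.38/0.325 = 1.17) and 1.9% at p = 0.05 (z = 0.45/0.218 = 2.06). Among imputed values, 12% vs 5% becomes about 12% vs 2%, so the arm difference is exaggerated.
- *Simulation* (361 per arm, 5–8% missing completely at random, uninformative covariates, three readings of the broken rounding line):

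| Path | Null rejection | Power |
|---|---|---|
| Rounded normal, two-sided p | 2.8–4.3% | 86–90% |
| Rounded normal, upper tail | about 6–8% | – |
| Binary imputation, upper tail | 4.9–5.6% | 91–92% |

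**(3) Appendix 3 GLMM.** A row of n events has response 1 and count n, so it is read as 1 event in n trials. A site and arm therefore contributes at most one event. With 361 per arm spread evenly over S sites, the expected number of events counted per arm is S·[1 − (1 − p/S)^361].

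| | Control | Embolization | OR |
|---|---|---|---|
| True (361 × rate) | 43.3 | 18.1 | 0.39 |
| As coded, S = 30 | 22.9 | 13.6 | (13.6/347.4)/(22.9/338.1) ≈ 0.58 |
| As coded, S = 40 | 26.5 | 14.5 | (14.5/346.5)/(26.5/334.5) ≈ 0.53 |

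Simulated trials (722 patients, 2,000 runs, no site variance) give an average OR of 0.56 instead of 0.38 with 30 sites and 0.52 instead of 0.38 with 40. Significance falls from 94% to 27% and from 93% to 46%.

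**The case against.** These are labelled example programs, and the text, Table 4, the protocol and Appendix 3 all name or code CMH. A programmer would notice that two stratum results cannot fill a single cell in Table 4. Some asterisks, a bracket and even the response variable in the CMH block may have been lost in reading the PDF. All of that is fair, and lost symbols are not counted here. It does not explain a different option, a different output table and a shared dataset name.

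Three stronger readings are tempting, and the documents do not support them.
- *The wrong primary test will be run, or type I error is inflated.* The planned test is not in doubt, and the unstratified branch rejects at or below nominal.
- *The GLMM in 8.2.3.2 miscounts in every case.* Its multivariable version fits age and baseline hematoma volume, which need essentially one row per patient. With a count of 1 on each row the coding is correct. The fault arises there only if the count is the per-level frequency that the input list defines. In Appendix 3 the code itself builds that frequency. Even there, the response is also listed as a class variable, so it is not certain that the step runs as modelled.
- *The doubled p-value will be reported under imputation.* No passage says so. The step is missing, not specified wrongly, and the default would be conservative.

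The missing STRATA would probably stop the run rather than bias it silently. The 6–8% figure depends on how a garbled line is read and on the missingness assumptions.

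**Conclusion.** The point holds as a set of code-to-text conflicts, at the low end of what should be fixed before database lock. Certain from the documents: the block headed CMH does not request CMH, the number of imputations is stated two ways, the Appendix 3 pooling has no p-value step, and its GLMM counts within response level. The effect on the primary p-value is either negligible or a missing number. The imputation items matter only if about 5% or more of primary endpoints are missing.

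The largest numerical effect, an OR of about 0.52–0.57 instead of 0.38, concerns a sensitivity analysis under imputation. It assumes equal expected site sizes and no between-site variance, so how often significance is lost depends on the real site structure. No false positive is shown for the plan as written.

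**What to change.** 1. **8.2.3.1:** request `strata*trtan*aval / cmh`, output the CMH table to a dataset with its own name, and point the results section to it, in line with Protocol 7.3.1 and Appendix 3.
2. **8.2.1 and Appendix 3:** state one number of imputations and carry STRATA through the transpose. Report the upper-tail p from the pooled score: half the two-sided p if the pooled z is positive, otherwise 1 minus half. Make this change together with a logistic (FCS) imputation of the binary outcome, and amend the MCMC wording in 8.2.1. Changing the tail alone could raise null rejection under the simulated assumptions. Check the rounding line and the Wilson-Hilferty bracket against the source file.
3. **8.2.3.2 and Appendix 3:** fit the GLMM to one 0/1 row per patient with a binary distribution and logit link, or use the count as a frequency. Keep the stated model of group plus random site. Check the ordinal mRS code in 9.1.2.3, which reuses the same form.

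The cost is code and SAP wording, before database lock. No new data or patients are needed.
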